Official Title: Efficacy of a Peri-Operative Surgical-Site, Multimodal Drug Injection in Pediatric Patients with Cerebral Palsy Undergoing Hip Surgery: A Randomized Controlled Trial.

NCT: NCT04074265

Date of Document: 1/4/2024

Study Title:

Efficacy of a Peri-Operative Surgical-Site, Multimodal Drug Injection in Pediatric Patients with Cerebral Palsy Undergoing Hip Surgery: A Randomized Controlled Trial.

Study Design:

This study is a prospective, randomized controlled trial with 2 parallel arms. Patients will be randomly assigned to the 2 treatment groups: surgical-site injection with ropivacaine, ketorolac, and epinephrine, or surgical-site injection with normal saline. Randomization will be performed via random number generator and will be carried out by a research associate who will not participate in study recruitment or outcomes assessment. Allocations will be concealed on a password-protected database accessible only to the research associate. Patients, surgeons, and nursing staff who perform post-operative assessments will be blinded to treatment allocation.

Participants:

Patients will be eligible to be included in this study if they are under the age of 18 years, have a known diagnosis of cerebral palsy, and are scheduled to undergo surgery of the proximal femur (specifically, unilateral or bilateral proximal femoral osteotomy for hip dysplasia). Patients will be recruited from both UCLA/Orthopaedic Institute for Children and Lurie Children's Hospital of Chicago. Patients and parents/guardians will be asked at their pre-operative clinic visit if they would like to participate in the study. They will be provided with the informed consent form at their pre-operative visit in order to allow them time to review the information prior to signing consent. Informed consent for the study will then be obtained in the pre-operative holding area prior to surgery. Patients will be excluded from the study if they have ongoing pre-operative opioid use, or a history of an allergic reaction to any of the components of the pain injection.

Surgical Procedure:

Patients undergoing unilateral or bilateral hip proximal femoral osteotomies will be included in the study. All patients will be treated with standard-of-care techniques chosen by the treating surgeon. The addition of pelvic osteotomies and/or soft tissue procedures will be at the discretion of the treating surgeon and will not exclude the patient from the study. Written consent will be obtained for all patients prior to the surgical procedure. Parental consent will be obtained, in addition to patient assent for all patients of appropriate age and intellectual capability. All patients will have a general anesthetic with a lumbar epidural. No preemptive scheduled analgesic regimen will be employed. All medications administered during induction and maintenance of anesthesia will be managed by the anesthesiologist and titrated at their discretion.

The local anesthetic group will be injected with ropivacaine 2mg/mL (3mg/kg), epinephrine 1mg/mL (0.5mg), and ketorolac 30mg/mL (0.5mg/kg). If bilateral hips are involved, the total amount will be split evenly between the two sides. The control group will receive equivalent volumes of 0.9% sodium chloride solution (these volumes will be calculated based on the volumes of medication the patient would have received had they been assigned to the cocktail group). The injections will be performed while the patient is still under general anesthesia,

following wound closure, and medications will be injected evenly between the deep and superficial tissues in an extra-articular pattern (no injection of the synovium or capsule). All injections will be performed using a 20-gauge needle. The injection medications will be placed in a sterile cup. The surgical technician will fill syringes from the labeled cup, which will be handed to the surgeon for immediate administration.

Post-Operative Protocol:

The epidural anesthesia will be started at the discretion of the attending anesthesiologist either before or on-arrival to the post-anesthesia care unit. Any additional medications administered during the immediate post-operative period in the post-anesthesia care unit will be prescribed by the attending anesthesiologist and will not be standardized. Beginning when the patient leaves the post-anesthesia care unit, all patients will be given the following pain regimen: acetaminophen (15mg/kg PO or per g-tube every 6 hours around the clock), ketorolac (0.5mg/kg IV every 8 hours for 3 doses) followed by ibuprofen (10mg/kg PO or per g-tube every 8 hours as needed for mild pain (pain score 1-3)), diazepam (0.1mg/kg PO or per g-tube every 6 hours around the clock for 36 hours followed by every 6 hours as needed for muscle spasms), and oxycodone (0.1mg/kg PO or per g-tube every 6 hours as needed for severe pain (pain score 7-10)). Nurses will be instructed to offer this as-needed medication to patients at standardized intervals every 4 hours when performing pain assessments. Additional medication for pain may be administered if the protocol does not result in adequate pain relief, at the discretion of the treating physician. The epidural will be titrated by the acute pain anesthesiology team for inadequate pain control, and all epidurals will be discontinued the morning of post-operative day two. All patients will be discharged on a standardized medication regimen as follows: diazepam (0.1mg/kg PO or per g-tube every 6 hours for 14 days), oxycodone (0.1mg/kg PO or per g-tube every 6 hours as needed for severe pain, 20 doses), acetaminophen (15mg/kg PO or per g-tube every 6 hours for 14 days), and ibuprofen (10mg/kg PO or per g-tube every 8 hours for 14 days). Inpatient and outpatient narcotic consumption will be recorded as morphine equivalents.

All other aspects of post-operative care, including (but not limited to) physical therapy, weight bearing status, mobilization, and bracing will be decided on a case-by-case basis by the treating surgeon.

Data Collection and Protection:

Data will be collected by IRB-approved research personnel via access to the medical record. Personal identifying information collected will include name, date of birth, medical record number, and telephone number. All data will be labeled with a code that can be linked to this personal identifying information. Data will be collected only from the hospitalization following the surgical procedure and from the first post-operative visit. This data will include: narcotic consumption, pain scores, complications or adverse events, and re-admission in the immediate post-operative period (first two weeks post-operatively). All data will be stored on a secure, encrypted data storage device or password protected and encrypted internet-based storage device.

Outcome Measures:

The primary outcome measure will be total narcotic consumption in the first 48 hours after surgery. Narcotic consumption will be recorded in the medical record while in the post-anesthesia care unit and while inpatient and will be converted into morphine equivalents according to a conversion table. The secondary outcome will be pain scores during inpatient hospitalization following the surgical procedure. Pain score assessments will be completed in the post-anesthesia care unit, and every 4 hours following the surgical procedure. Scores will be collected by nursing staff on the inpatient ward who are blinded to treatment allocation and recorded in the electronic medical record. The type of pain score collection will vary based on patient age and level of intellectual disability. In verbal children, either the VAS or FACES pain scale will be employed. In non-verbal children, the FLACC scale will be employed.

Additional secondary outcome measures will include total narcotic consumption following hospital discharge, length of stay, parent satisfaction scores, and complications. Patients will be instructed to bring their medications with them to their first post-operative visit, and outpatient narcotic use will be recorded based on amount of medication remaining. This will also be converted into morphine equivalents according to the same conversion table. Parent satisfaction scores will be based on a standardized questionnaire taken by parents in person at the first post-operative clinic visit aimed to assess their satisfaction with their child's pain management perioperatively.

Statistical Analysis Plan

Outcome measures will be analyzed using a two-tailed t-test or a non-parametric Mann-Whitney test for quantitative variables; a Fischer exact test was used for categorical variables. Further, while a t-test will be utilized to demonstrate differences in narcotic consumption and average pain scores during *discrete, comparable, clinically-relevant measures of time*, mixed effects modeling will be utilized to further analyze narcotic consumption and pain scores *over time*. Statistical significance will be defined as p<0.05.

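### Unilateral and bilateral cases are pooled and compared without adjustment: valid, but possibly less precise than it could be, and its average effect depends on a case mix that the plan does not undertake to report

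*Combined protocol and SAP*

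**What the plan says.** Under Surgical Procedure: "Patients undergoing unilateral or bilateral hip proximal femoral osteotomies will be included in the study". The same section leaves further surgery open: "The addition of pelvic osteotomies and/or soft tissue procedures will be at the discretion of the treating surgeon and will not exclude the patient". The active injection is one total per patient (ropivacaine 3 mg/kg, ketorolac 0.5 mg/kg, epinephrine 0.5 mg), and "If bilateral hips are involved, the total amount will be split evenly between the two sides". Controls receive matching volumes of saline.

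Under Study Design: "Randomization will be performed via random number generator". No stratification factor, blocking or minimisation is mentioned.

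Under Outcome Measures, the primary outcome is each patient's narcotic total over the first 48 hours, in morphine equivalents. Under Statistical Analysis Plan: "Outcome measures will be analyzed using a two-tailed t-test or a non-parametric Mann-Whitney test for quantitative variables". A mixed effects model over time is added, with no covariates named. No analysis by laterality or by type of procedure is planned, and neither item appears in the data listed under Data Collection and Protection.

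**The concern.** Laterality determines two things at once: how many femurs are operated on and how much of the injection reaches each. Either could affect opioid use, yet neither the stated allocation method nor the stated analysis refers to laterality or to added pelvic surgery.

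Two things are at stake. The first is precision: if more extensive surgery means more opioid, the variation between unilateral and bilateral cases stays in the error term of an unadjusted test. The second is interpretation: if the injection works less well when split, the pooled estimate depends on the share of bilateral cases, and a reader who is not told that share cannot tell what the average refers to.

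**Working it through.** The documents state no sample size, SD, target effect or expected bilateral share, so there is no figure of the plan's own to reproduce. Step 1 uses the documents' numbers. Steps 2 to 4 are illustrations on stated assumptions.

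**1. Amount per hip (Surgical Procedure).**

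| | Unilateral, per hip | Bilateral, per hip | Total per patient |
|---|---|---|---|
| Ropivacaine | 3 mg/kg | 3/2 = 1.5 mg/kg | 3 mg/kg |
| Ketorolac | 0.5 mg/kg | 0.5/2 = 0.25 mg/kg | 0.5 mg/kg |
| Epinephrine | 0.5 mg | 0.5/2 = 0.25 mg | 0.5 mg |

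The amount per hip halves; the total does not depend on laterality.

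**2. Precision.** Let p be the bilateral share and D the bilateral-minus-unilateral difference in opioid use, in within-group SDs. The unadjusted variance is 1 + p(1−p)D², so adjustment removes p(1−p)D² / [1 + p(1−p)D²]. With p = 0.5:
- D = 0: 0/1 = 0%
- D = 0.5: 0.0625/1.0625 = 6%
- D = 1.0: 0.25/1.25 = 20%

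With p = 0.3 or 0.7 the last two become 0.0525/1.0525 = 5% and 0.21/1.21 = 17%.

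For scale, assume a treatment effect of 0.8 within-group SD, two-sided 5% and 80% power. Then n per arm = 2(1.96 + 0.84)² × variance / 0.8². This gives 25 per arm with adjustment (or if D = 0). Without adjustment at p = 0.5 it gives 27 for D = 0.5 and 31 for D = 1.0. Power at 25 per arm goes from 81% to 78% and 72%.

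**3. Dependence on case mix.** Let r be the bilateral effect as a fraction of the unilateral effect. Pooled effect / unilateral effect = 1 − p(1−r). With p = 0.5:
- r = 0.5: 1 − 0.25 = 0.75
- r = 1: 1.0 (no dilution)

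At r = 0.5 the ratio is 0.85 for p = 0.3 and 0.65 for p = 0.7. Covariate adjustment does not change this ratio; only reporting the case mix and the two effects makes it visible.

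**4. What a laterality comparison could show.** Assume 25 per arm and half bilateral, so four cells of 12.5. The interaction SE is √(4/12.5) = 0.57 SD. Against an assumed interaction of 0.4 SD (0.8 unilateral, 0.4 bilateral), 0.4/0.57 is about 0.7 standard errors, and power at two-sided 5% is about 11%.

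**The case against.** The strongest reply is that the design answers a coherent question. A fixed total is compared with matched-volume saline on a patient-level outcome, and randomisation protects that average whatever the mix of cases. This stands, and it rules out several stronger readings that a reader might infer.

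- *The pooling biases or invalidates the primary comparison.* It does not. The unadjusted test is valid and the contrast is unbiased in expectation.
- *Two treatment intensities are being mixed.* This is true per hip only; the total per patient does not depend on laterality.
- *Extent of surgery is a main prognostic factor.* It is plausible, but no figure in the documents shows it. Every patient also has a lumbar epidural, titrated for inadequate pain control until the morning of post-operative day two, which could weaken the link over 48 hours. That is why D = 0 belongs in the range.
- *Chance imbalance is a further harm.* With fixed arms of 25 and half bilateral, a gap of 20 percentage points or more has about a 20% chance, and at D = 1.0 a 20-point gap shifts the contrast by 0.2 SD. But the unadjusted SE, √(2 × 1.25/25) = 0.32 SD, already allows for such shifts; 0.2/0.32 is about 0.63 of one SE. Counting it beside the precision loss counts it twice.
- *A difference between unilateral and bilateral effects would show that splitting the dose matters.* It could not. Dose per hip and number of operated hips are fully confounded, and step 4 shows how little power there would be.
- *The allocation is unstratified and laterality will not be collected.* The documents are silent on the first. The data list is not exhaustive either: it omits length of stay and parent satisfaction, which are stated outcomes. Data come from the medical record, so both factors should be obtainable.

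What the reply does not remove is that the stated analysis names no covariate, although suitable ones are at hand.

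**Conclusion.** The point holds as a recommended improvement, not as a flaw that undermines the trial. The plan pools cases that differ in operated sites and in amount per hip, names no covariate for the primary comparison, and does not undertake to report the mix. With half the cases bilateral, the avoidable variance is 0% to 20% for an assumed difference of 0 to 1.0 SD, and the pooled effect is 0.75 to 1.0 of the unilateral effect for an assumed bilateral effect of half to all of it. All of these rest on assumed values; only the halving per hip comes from the documents.

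Adjustment is safe. Laterality is part of the eligibility description and known when surgery is scheduled. Pelvic osteotomy is done before the injection, which follows wound closure, by a surgeon who is blinded. The injection can affect neither. Because pelvic osteotomy is at the surgeon's discretion and the documents do not say that it is settled before randomisation, it is suited to adjustment but not assuredly to stratification.

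**What to change.** 1. Record laterality and pelvic osteotomy (yes/no) from the operative note.
2. Before unblinding, pre-specify the primary analysis as a linear model (ANCOVA) of 48-hour morphine equivalents on treatment, laterality and pelvic osteotomy. Name a rank-based or transformed-outcome version for skewed data, since the Mann-Whitney test has no direct covariate adjustment.
3. Stratify any remaining allocation by planned laterality. The document is dated 1/4/2024 and does not say how far allocation has gone; if it is complete, the other steps still apply.
4. Report laterality and pelvic osteotomy by arm.
5. Report the unilateral and bilateral effects and the interaction with its interval as exploratory, and state that a difference cannot be attributed to dose per hip.

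The cost is SAP wording, two variables, one or two degrees of freedom, and an exploratory interaction that will be imprecise. No change to the injection is implied.

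### The pain-titrated epidural covers most of the 48-hour narcotic window, but its dose is in no named outcome or analysis

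*Combined protocol and SAP*

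**What the plan says.** The Surgical Procedure section states: "All patients will have a general anesthetic with a lumbar epidural". The Post-Operative Protocol section adds: "The epidural will be titrated by the acute pain anesthesiology team for inadequate pain control, and all epidurals will be discontinued" on the morning of the second post-operative day. It gives no drug, concentration, rate or titration threshold.

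The same section orders "oxycodone (0.1mg/kg PO or per g-tube every 6 hours as needed for severe pain (pain score 7-10", and ties as-needed ibuprofen to scores 1 to 3. No as-needed drug is tied to scores 4 to 6. Beyond these orders, "Additional medication for pain may be administered if the protocol does not result in adequate pain relief", and drugs given earlier "in the post-anesthesia care unit will be prescribed by the attending anesthesiologist and will not be standardized".

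Outcome Measures makes 48-hour narcotic use, converted to morphine equivalents by a conversion table, the primary outcome. Inpatient pain scores, taken every 4 hours by blinded nurses, are the secondary outcome. Data Collection and Protection says: "This data will include: narcotic consumption, pain scores, complications or adverse events, and re-admission in the immediate post-operative period". That list is not exhaustive, since length of stay and parent satisfaction are outcomes but are not on it. Still, epidural dose is neither on the list nor among the outcomes.

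The Statistical Analysis Plan compares arms by t-test or Mann-Whitney test, with mixed effects models over time. It mentions neither epidural dose nor hospital and does not state the model covariates. Two hospitals recruit, and Study Design describes no stratification.

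**The concern.** A child in pain can be helped in two main ways: by narcotic, which the primary endpoint counts, or by more epidural drug, which no planned analysis uses. If the injection works, saline children may have their epidurals turned up more often. That can keep them below the oxycodone threshold and change the narcotic difference between arms. It can also pull the pain scores together. Randomization and blinding do not prevent this, because titration is a response to treatment after randomization.

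What is at stake is interpretation. If narcotic use does not differ, or narcotic and pain scores point different ways, nothing planned shows whether rescue moved to the epidural. If the epidural contains an opioid, the primary endpoint also depends on whether that opioid is counted, and the plan does not say.

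**Working it through.** The documents give no sample size, SD, effect size, score distribution or titration rule, so there is no planned figure to reproduce. Steps 2 to 4 are illustrations under stated assumptions.

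**1. Overlap of the epidural with the endpoint window.** Hours of overlap = min(48, 48 − hour surgery ends + hour epidural stops). Clock times are assumed.
- Surgery ending at 14:00, stop at 08:00: 48 − 14 + 8 = 42 h, or 87.5% of the window.
- Surgery ending between 10:00 and 18:00, stop between 06:00 and 12:00: 36 to 48 h, or 75% to 100%.

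**2. Effect on narcotic use when the benefit lasts 48 h.** From the plan: 48/4 = 12 assessments, and one oxycodone dose at a score of 7 or more if at least 6 h have passed since the last. Assumed: control mean 4, between-child SD 1.5, within-child SD 1.32, scores rounded and limited to 0–10, injection 1 point lower throughout. Each score at or above the titration threshold lowers later scores by 0.5 or 1 point (maximum 3) until the epidural effect ends. Epidural opioid is not counted.

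n per arm = 2(1.96 + 0.8416)² × (SD/difference)². Power at 74 per arm = Φ(√(74/2) × difference/SD − 1.96). The inputs shown are rounded, so n agrees to within one child. Paired values are for the 0.5- and 1-point steps.

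| Titration | Difference (doses) | SD | n per arm | Power at 74 |
|---|---|---|---|---|
| None | 0.576 | 1.247 | 74 | 80% |
| At 4 or more, ends 36 h | 0.312; 0.263 | 0.782; 0.680 | 99; 105 | 68%; 65% |
| At 4 or more, ends 40 h | 0.264; 0.214 | 0.683; 0.580 | 105; 116 | 65%; 61% |
| At 4 or more, ends 48 h | 0.165; 0.115 | 0.499; 0.393 | 143; 184 | 52%; 43% |

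An end at 44 h gives 120–138 per arm. If titration occurs only at 7 or more, n is 73–74, so nothing is lost. With control mean 5, n is 53 without titration and 67–76 with titration at 4 or more ending at 36–40 h. Mean pain score (control mean 4) needs 38 per arm without titration and 45 at most with it.

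**3. A shorter benefit.** Nothing in the documents says a single injection works for 48 h. The other assumptions are unchanged, with titration at 4 or more.
- 24 h benefit, epidural ending at 40 h: narcotic n goes from about 360 to 520–730 per arm, which is a loss.
- 12 h benefit, epidural ending between 36 and 48 h: narcotic n goes from about 1,600 to 535–1,654, so the loss vanishes or reverses. Pain-score n goes from 621 to 1,338–5,065.

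Titration shrinks the SD of narcotic use as well as the difference, so their ratio can move either way.

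**4. Epidural opioid.** If it exists and is counted, extra titration in the saline arm adds narcotic to that arm and works against the shrinkage in step 2.

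**5. Hospital.** With a 50:50 split and a hospital difference of r within-hospital SDs, the unadjusted variance is 1 + r²/4 times the within-hospital variance:
- r = 0.25: 1.016, about 2% more children
- r = 0.5: 1.063, about 6%
- r = 1: 1.25, or 25%

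**The case against.** The strongest reply is that pain scores already guard against a misreading. They are collected every 4 hours by blinded nurses and analysed. In the 48-hour-benefit model with titration at 4 or more and 74 per arm, pain scores were significant in 91–94% of trials with a non-significant narcotic result. Both outcomes were null in 2.2–4.4%, against 2.2% without titration. This stands for a long benefit, but not for a 12-hour one, where pain scores lose power. Nor can pain scores show whether rescue moved to the epidural.

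A second reply is that the figures rest on an invented threshold and duration. That also stands: 74 per arm is not this trial's size, and the figures establish no direction for this trial.

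A third is that total narcotic, read plainly, includes any epidural opioid. That may be so, but the conversion table is not in the documents and no rule is stated. This is missing detail, as is the absence of an as-needed drug for scores 4 to 6. The hospital term is a separate matter of precision.

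A reader might infer that the whole endpoint is measured under the epidural. The stop time does not support that: up to about 12 of the 48 hours may follow removal under the assumed clock times.

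**Conclusion.** The concern holds as a gap in measurement and interpretation. A rescue route that treatment itself can affect runs through most, not necessarily all, of the primary window, and its dose is in no named outcome or analysis. Size and direction are unknown. They depend on the titration threshold, how long the injection works, and whether epidural opioid is counted. The illustrations range from no loss, through a fall in power from 80% to 43%, to a gain for narcotic with a loss for pain scores.

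A reader might infer that a working injection would go undetected, or that a null narcotic result would be reported as no analgesic effect. The documents do not support either: pain scores are a planned secondary outcome, and nothing in the plan commits to that reading. Type I error is unaffected, and narcotic sparing on top of standard care stays a legitimate primary endpoint. The change is worth making because it is cheap and improves what the trial can conclude.

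**What to change.** 1. For 0–48 h, abstract epidural drug, concentration, rate changes and boluses, and all other discretionary analgesics. Before unblinding, pre-specify epidural volume per kg, or the number of upward titrations, by arm as a supportive outcome read with narcotic and pain scores. A yes/no rescue indicator saturates: 93–94% against 81–82% in the 48-hour-benefit model (control mean 4, titration at 4 or more, epidural ending at 36–40 h). It needs 119–125 per arm, against 43–50 for the titration count. Do not adjust the primary analysis for epidural dose, because treatment affects it. If narcotic does not differ but epidural use is higher with saline, report that no narcotic sparing was shown and that rescue shifted to the epidural.
2. If the epidural contains an opioid, fix before unblinding whether it enters the morphine-equivalent total, and report the other version as a sensitivity analysis.
3. Separately, include hospital in the primary analysis (linear model, or van Elteren test if non-parametric) and in the mixed model.

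The cost is low. The medical record is already the data source, so item 1 adds a few abstraction fields, feasible even after enrolment, and one supportive analysis. Items 2 and 3 are a few lines in the SAP. The analgesic orders do not change.

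### The two narcotic totals have no stated per-kg unit or weight adjustment although protocol oxycodone is dosed per kg; the planned tests stay valid but may lose precision

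*Combined protocol and SAP*

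**What the plan says.** Under Outcome Measures: "The primary outcome measure will be total narcotic consumption in the first 48 hours after surgery". On its measurement: "Narcotic consumption will be recorded in the medical record while in the post-anesthesia care unit and while inpatient and will be converted into morphine equivalents". The secondary outcomes include "total narcotic consumption following hospital discharge", converted with the same table. No per-kg unit is stated for either total, and the conversion table is not reproduced.

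Under Post-Operative Protocol, the ward regimen lists "oxycodone (0.1mg/kg PO or per g-tube every 6 hours as needed for severe pain (pain score 7-10" and the discharge regimen "oxycodone (0.1mg/kg PO or per g-tube every 6 hours as needed for severe pain, 20 doses". Opioids in the recovery room are not standardized, and further pain medication is left to the treating physician.

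Under Participants, patients must be younger than 18; no lower limit of age or weight is given.

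The Statistical Analysis Plan says "Outcome measures will be analyzed using a two-tailed t-test or a non-parametric Mann-Whitney test for quantitative variables" and adds that "mixed effects modeling will be utilized to further analyze narcotic consumption and pain scores" over time. No covariate is named for that model.

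**The concern.** For protocol oxycodone, the amount recorded is the number of doses times 0.1 mg/kg times weight. The number of doses reflects pain and may respond to the injection; weight cannot. An unscaled, unadjusted total therefore carries variation that treatment does not influence. If that variation is large relative to the variation in use per kg, a real opioid-sparing effect is more likely to be missed. A t-test or Mann-Whitney test cannot remove it. The mixed model could, but the plan does not say that it will, and it is presented as a further analysis rather than a replacement for the comparison of totals.

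**Working it through.** **No plan figure to reproduce.** The documents give no sample size, power, SD or weight distribution. From the documents come the 0.1 mg/kg dose, the 20-dose discharge supply and the two-sided 0.05 level. Everything else below is an assumption.

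**Dose arithmetic.** At assumed weights of 15 and 45 kg, one protocol dose is 0.1 × 15 = 1.5 mg and 0.1 × 45 = 4.5 mg of oxycodone. The full discharge supply is 20 × 0.1 = 2.0 mg/kg, i.e. 30 mg and 90 mg.

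**Model.** Let use = K(fW + 1 − f), where W is weight and K is use net of weight. Both have mean 1 and are independent; f is the share of use that scales with weight. Relative to no weight variation, the variance ratios are:

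- raw total: 1 + f²·CVw²·(1 + 1/CVk²)
- weight-adjusted total: 1 + f²·CVw²

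The difference, f²·CVw²/CVk², is what adjustment removes. With 80% power if weight did not vary, power = P(Z > 1.96 − 2.80/√ratio) plus the negligible opposite tail. Extra patients needed by the raw analysis = raw ratio/adjusted ratio − 1.

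**Two corners at f = 1.**

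- CVw 0.55, CVk 0.6: raw 1 + 0.3025 × (1 + 1/0.36) = 2.143, power 48.2%; adjusted 1.3025, power 69.0%. Gain 20.8 points; 2.143/1.3025 − 1 = 65% more patients.
- CVw 0.35, CVk 1.5: raw 1.177, power 73.3%; adjusted 1.1225, power 75.3%. Gain 2.0 points; 5% more patients.

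**Grid** (CVw 0.35–0.55, CVk 0.6–1.5):

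| Share f | Raw power | Adjusted power | Gain (points) | Extra patients |
|---|---|---|---|---|
| 100% | 48–73% | 69–75% | 2–21 | 5–65% |
| 75% | 59–76% | 74–77% | 1–15 | 3–40% |
| 50% | 70–78% | 77–79% | 0.5–7.5 | 1–20% |
| 25% | 77–80% | 79–80% | 0.1–2 | 0.3–5% |

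At f = 0 adjustment neither gains nor loses.

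**Narrower weight spread.** At CVw 0.2 and f = 1 the gain is 0.6–4 points and the extra patients 2–11%. At f = 0.5 the gain is about 0.2–1 point.

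**Per-kg use that falls with weight.** Let every dose scale with weight, but let per-kg use fall as W^−a, with W lognormal. Extra patients needed by the raw analysis:

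| CVw, CVk | Independent | a = 0.5 | a = 0.75 |
|---|---|---|---|
| 0.55, 0.6 | 65% | 17% | 4% |
| 0.45, 0.8 | 26% | 7% | 2% |
| 0.35, 1.0 | 11% | 3% | 1% |

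**Per-kg outcome as an alternative.** In the grid model its power is 80% at f = 1, 76–79% at 75%, 67–78% at 50%, 57–76% at 25% and 48–73% at f = 0, where the raw total keeps 80%. Under W^−a, with σ² = ln(1 + CVw²), the squared CV is (1 + CVk²)·exp((1 − a)²σ²) − 1 for the total and (1 + CVk²)·exp(a²σ²) − 1 per kg. These are equal at a = 0.5. At a = 0.75, CVw 0.55 and CVk 0.6, the CVs are 0.62 for the total and 0.76 per kg.

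**Simulation** (3000 runs, assumed 60 per arm, f = 1, 0.5 and 0.25). Type I error was 4.6–5.3% for the raw t-test, 4.5–5.7% for the raw Mann-Whitney test, and 4.2–5.1% for the weight model with HC3 errors. Power at f = 1, raw t-test against weight model:

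- 54% against 74% (CVw 0.55, CVk 0.6)
- 66% against 76% (0.45, 0.8)
- 70% against 74% (0.35, 1.0)
- 69% against 70% (0.45, 1.5, with 30% zero users)

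In that last case the raw and weight-adjusted rank analyses both gave 31%.

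**The case against.** The strongest case against is that no material loss has been shown. Oxycodone is given only for scores of 7–10, alongside an epidural that runs until the morning of day two, so many totals may be low or zero; the simulated case with 30% zeros shows almost no gain. Recovery-room and discretionary opioids need not scale with weight. Per-kg use may fall as weight rises, and eligibility under 18 says little about the weight spread actually enrolled. All of this stands, and it is why the size is given as a range starting at negligible.

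It can also be said that the word total does not exclude mg/kg and that an unlisted covariate is not a forbidden one. That is fair: the supported statement is that scaling and adjustment are unspecified. But the two named tests cannot adjust for weight, so silence on the unit leaves the primary comparison exposed.

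Three stronger inferences are tempting and not supported.

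- *The comparison is biased or its error rate inflated.* Randomization balances weight on average, and simulated type I error stayed near 5%. A chance imbalance could move a single estimate in a small trial, but that is not bias.
- *Weight will not be collected, because the data list omits it.* That list also omits length of stay and parent satisfaction, both named outcomes, so it is not exhaustive. Weight must be known for every mg/kg dose and for the saline volumes: "these volumes will be calculated based on the volumes of medication the patient would have received had they been assigned to the cocktail group".
- *Both outcomes should simply be expressed per kg.* A standardized 0.1 mg/kg discharge prescription does not make the number of doses taken independent of weight. Per-kg scaling can lose power after discharge as well as in the first 48 hours.

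**Conclusion.** The point holds as a matter of efficiency. Neither scaling nor adjustment for weight is specified for the two narcotic totals, and the planned unadjusted tests are valid but may be less precise than they need be. The loss cannot be derived from the documents. It is negligible if few opioids scale with weight, many totals are zero, the weight spread is narrow, or per-kg use falls as weight rises. It reaches about 21 power points only with full scaling, per-kg use independent of weight, weight CV 0.55 and per-kg CV 0.6. A reader should not take that upper figure as the expected loss: all CVs, the scaled share, the independence of per-kg use and weight, and the 80% baseline are assumptions. The case for acting rests on low cost, not on a demonstrated large loss.

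**What to change.** Before unblinded analysis:

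- In the SAP, pre-specify the analysis of both totals (0–48 hours and post-discharge) as a linear model of morphine equivalents on arm and dosing weight, with robust standard errors because the totals may be skewed.
- Include dosing weight in the mixed model for narcotic consumption.
- Keep the planned unadjusted comparison as supporting, and report morphine equivalents per kg as a sensitivity analysis for both outcomes.
- In Outcome Measures, state the unit of both totals, and record dosing weight as a data field.

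This costs a few sentences and one field for a value already needed for dosing. No patients or procedures are added. The downside is one covariate and a slightly more complex model than a two-sample test.
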